# 3 Study Design

This study is a non-randomized, observational, phase IV, multi-site pilot study to investigate the compliance with and perceptions of treatment, as well as HRQOL in surgically resected melanoma patients undergoing HDI or PEG IFN therapy. After discussion with their treating physician, patients will receive 1 of 2 approved adjuvant therapies for melanoma:

- 1. Cohort A: high-dose interferon alfa (HDI, Intron® A)
- 2. Cohort B: pegylated alfa-interferon 2b (PEG IFN, SylatronTM)

Although the study is not randomized, in order to attempt to discern a difference between the groups, a maximum of a 60:40 split will be allowed on the protocol. This means that a

maximum of 60% of patients will be permitted on either arm and if achieved, that particular arm will be capped at 60%.

Each treatment arm will have a pretreatment phase (within 4 weeks/28 days of starting the induction phase (4 weeks of HDI or 8 weeks of PEG IFN), a maintenance phase (treatment administration at specified times up to 1 year), and an end-of-study assessment, conducted within 21 days of discontinuation of study treatment.

The primary endpoint of this study is to compare compliance with treatment of HDI and PEG IFN. Patients will complete drug administration diaries to track compliance with the recommended dosing schedule. Secondary endpoints include comparing treatment perceptions and HRQOL between treatment groups, comparing the frequency of Grade 3 and Grade 4 adverse events (AEs) in each treatment arm, and evaluating the reasons for patients' choice of treatment with HDI or PEG IFN through the use of the Interferon Preference Questionnaire

Patients receiving HDI will complete the CCSQ and FACT-BRM at baseline, every 2 weeks during the induction phase and monthly during the maintenance phase (beginning at Day 29) for up to 1 year. Patients receiving PEG IFN will complete the CCSQ and FACT-BRM at baseline, 2 weeks, 4 weeks, 6 weeks, and monthly during the maintenance phase (beginning at Day 57) for up to 1 year. Adverse events will be monitored throughout the study. Any dose adjustments based on toxicities will be made according to investigator judgment and the package insert for each product. Patients will also be queried to determine the most important reasons for choice of treatment with HDI versus PEG IFN.

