- j Patients will be instructed to record details on the receipt of HDI in the drug administration diary and will return the diary to the site at the subsequent visit. These diaries will capture the onset of AEs in relationship to the day of drug administration.

Patients should be seen for all visits on the designated day or as close as possible to the designated day. Please note that the  $\pm 1$  week interval in the Maintenance Phase of the study is proposed as a guide. Visits falling outside this window should not lead to automatic patient discontinuation.

All data obtained from the assessments listed in the schedule of events must be supported in the patient's source documentation.

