# 13 Appendices

# 13.1 Chemotherapy Convenience and Satisfaction Questionnaire (CCSQ)

Below is a list of statements that people receiving chemotherapy like yours have said are important. For each statement, please choose the reply that best fits your experience with receiving chemotherapy, and circle the number corresponding to your reply.

"Chemotherapy" means the drug(s) you receive to treat your cancer or tumor.

	Chemotherapy Experience - 1	Not at all	A little bit	Some- what	Quite a bit	Very Much
CS1	Chemotherapy treatment takes up my time .	0	1	2	3	4
CS2	My chemotherapy treatment takes up my family's time .	0	1	2	3	4
CS3	I worry about side effects from chemotherapy treatment.	0	1	2	3	4
CS4	My chemotherapy treatment causes me physical pain.	0	1	2	3	4
CS5	Receiving chemotherapy is inconvenient.	0	1	2	3	4
CS6	I worry that my chemotherapy will not be effective.	0	1	2	3	4
CS7	Chemotherapy treatment seems harmful to me.	0	1	2	3	4
CS8	My chemotherapy schedule is stressful to me .	0	1	2	3	4
CS9	My chemotherapy schedule is stressful to my family .	0	1	2	3	4
GP5	I am bothered by side effects of treatment.	0	1	2	3	4
	Please answer this last question about how you have felt this past week.					
GF7	I am content with the quality of my life right now.	0	1	2	3	4

Considering your experience with chemotherapy to date, please respond to the following questions.

	Chemotherapy Experience - 2	No, not at all	Yes, to some extent	Yes, for the most part	Yes, completely
CS 10	Are you satisfied with the current results of your chemotherapy?	0	1	2	3

		No	Maybe	Yes
CS 11	Would you recommend this chemotherapy to others with your illness?	0	1	2
CS 12	Would you choose this chemotherapy again?	0	1	2

		Poor	Fair	Good	Very Good	Excellent
CS 13	How would you rate this chemotherapy?	0	1	2	3	4

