Data Analysis -REVISED JULY 2023

Due to the study's pilot study design, sample size was not calculated formally. For both primary and secondary outcomes, descriptive data are presented (i.e., medians and ranges for continuous data, frequencies and percentages for categorical data).

Although the original data plan called for exploratory mixed randomized-repeated measures analysis of variance (ANOVA) to be conducted for the primary and two secondary outcomes, the pattern of missing data across patients at the designated time points was too prevalent (and appeared not to be missing at random) to ensure robust ANOVA results. Therefore, we reported separate non-parametric statistical outcomes when deemed feasible (i.e., adequate and balanced subgroup sample sizes) in an attempt to obtain as much information as possible about data trends and patterns. Because we were unable to capture within-subject correlations over time, as well as the treatment group*time interaction, our results should be interpreted accordingly.

The primary outcome was compliance with HDI and PEG IFN (i.e., percentage of doses taken based on total doses required over 53 weeks, as recorded in patient diaries), with a difference of 30% between groups deemed clinically relevant. We reported frequencies and percentages per week and an overall percentage of doses taken at the end of 53 weeks, with statistical analysis of this outcome.

Secondary outcomes were as follows (with different time points reported depending on the highest outcome frequencies):

- Comparison of the convenience and satisfaction with chemotherapy for patients on standard HDI versus PEG IFN using a chemotherapy convenience and satisfaction questionnaire (CCSQ), summation of items CS1 – GP5, with a 30% between-group difference deemed clinically relevant. Time points of comparison were baseline/week 1, week 3, week 13, week 25, and week 50.
- Item GF7, which assesses contentment with current quality of life, at baseline/week 1, week 3, week 13, week 25, and week 49.
- Item CS10, which assesses satisfaction with current results of chemotherapy, at week 1, week 3, week 13, week 25, week 37, and week 45.
- Items CS11 and CS12, which measure recommendation/choice of chemotherapy regimen, at week 1, week 3, week 13, week 25, week 37, and week 45.
- Item CS13, which rates the chemotherapy regimen overall, at week 1, week 3, week 13, week 25, week 37, and week 45.

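### The SAP picks secondary-outcome weeks after the data by highest frequency, so the last CCSQ sum and FACT-BRM comparison is at week 50, off the nominal schedule, while GF7 from the same CCSQ form is at week 49

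*SAP*

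**What the plan says.** The SAP (Data Analysis, secondary outcomes) lists its time points "with different time points reported depending on the highest outcome frequencies". It does not say whether frequency means completed forms or observed outcomes, and it gives no visit window. The listed weeks are:

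- CCSQ sum of CS1 to GP5, and in a separate bullet FACT-BRM: "Time points of comparison were baseline/week 1, week 3, week 13, week 25, and week 50".
- GF7: "at baseline/week 1, week 3, week 13, week 25, and week 49".
- CS10 to CS13 stop earlier. CS13, for instance, is the item "which rates the chemotherapy regimen overall, at week 1, week 3, week 13, week 25, week 37, and week 45".

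The protocol (section 9, secondary outcomes) used one set of points for the CCSQ sum and GF7: baseline, 2 weeks, 3, 6 and 12 months. FACT-BRM was to be handled in the same way as the sum. For the sum, use of the 12-month point depended on how much was missing.

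In Appendix 13.1, GF7 ("I am content with the quality of my life right now") is printed in the same block as CS1 to GP5. Section 3 schedules both questionnaires monthly in maintenance, from Day 29 for HDI; for PEG IFN it says "monthly during the maintenance phase (beginning at Day 57) for up to 1 year". Section 6 makes these time points mandatory. It adds that the ±1 week "interval in the Maintenance Phase of the study is proposed as a guide".

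**The concern.** The SAP is in the past tense and reports the pattern of missing data as already observed, so the weeks were chosen with the data in view. Two things follow.

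First, the late comparison can change with the week picked. This matters most for the CCSQ sum and FACT-BRM. The protocol planned inferential analysis of both, and the SAP still reports non-parametric tests where feasible at p < .05.

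Second, the sum and GF7 are filled in together, so one visit should supply both. Forms are due about four weeks apart, and a patient would rarely have one form dated in week 49 and another in week 50. Read literally, the two late summaries describe largely different patients, although a reader will take them as two parts of one questionnaire at one visit.

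**Working it through.** **Inputs.** Questionnaire days come from protocol section 3 and Tables 2 and 3. HDI: Days 1 and 15, then monthly from Day 29. PEG IFN: Days 1, 15, 29 and 43, then monthly from Day 57. The protocol does not define a month in days, so I assume 28 days and test 29, 30, 30.44 and 31. Table 3 footnote c starts PEG IFN maintenance at Day 29, against Day 57 in section 3 and in the questionnaire footnote. Those passages need reconciling, but on 28-day steps both starts give the same late visits.

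**Week convention.** Study week = floor((day − 1)/7) + 1. Day 1 is week 1 and Day 15 is week 3, which matches the SAP's week 1 and week 3. Week 49 is Days 337 to 343 and week 50 is Days 344 to 350.

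**28-day grid.** Visits fall on Day 29 + 28k.

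- Day 85 (k = 2) is week 13 and Day 169 (k = 5) is week 25.
- Day 253 (k = 8) is week 37 and Day 309 (k = 10) is week 45.
- Day 337 (k = 11) is week 49 and Day 365 (k = 12) is week 53.

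Every week that the SAP lists (1, 3, 13, 25, 37, 45, 49) is on this grid in both arms, except week 50.

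**Other month lengths, last two visits of the year.**

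| Step (days) | HDI | PEG IFN | Week-50 visit? |
|---|---|---|---|
| 28 | Day 337 (wk 49), 365 (wk 53) | Day 337 (wk 49), 365 (wk 53) | No |
| 29 | Day 319 (wk 46), 348 (wk 50) | Day 318 (wk 46), 347 (wk 50) | Yes, but weeks 37, 45 and 49 are then off grid |
| 30 | Day 329 (wk 47), 359 (wk 52) | Day 327 (wk 47), 357 (wk 51) | No |
| 30.44 | Day 333 (wk 48), 364 (wk 52) | Day 331 (wk 48), 361 (wk 52) | No |
| 31 | Day 339 (wk 49), 370 (wk 53) | Day 336 (wk 48), 367 (wk 53) | No |

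**Distance of week 50 from a visit.** On the 28-day grid, ±7 days around Day 337 is Days 330 to 344, and around Day 365 it starts at Day 358. So 1 of the 7 days of week 50 (Day 344) lies within the guide. With 30.44-day months the windows end at Day 340 (HDI) and Day 338 (PEG IFN), and the next ones start at Days 357 and 354, so no day does.

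**What single-week placement would do, if it was used.** Days 330 to 344 are 15 days: 7 in week 48, 7 in week 49 and 1 in week 50. The share of in-window forms outside week 49 depends entirely on how visits scatter:

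- even over ±7 days: 8/15 = 53%
- normal with SD 2 to 4 days: 40% to 47%
- normal with SD 1 day: about 31%
- even over 0 to 7 days late: 1/8 = 12.5%

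The documents give no scatter, so this quantity cannot be determined from them.

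**The case against.** The practical reach is narrow. Weeks 1, 3, 13 and 25 correspond to the protocol's first four points and are the same for the CCSQ sum, GF7 and FACT-BRM. Only the last point differs, by one week, and GF7 was always descriptive. The study is an exploratory pilot, and the SAP discloses both its selection rule and the missing data. All of this stands and limits the weight of the point. The protocol's allowance for missing data at 12 months covers leaving that point out, not substituting another week.

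Week 50 may also be innocent. Induction delays move later assessments, and the synopsis includes both questionnaires at an end-of-study visit within 21 days of stopping treatment. Valid forms can therefore fall there. A slip is possible too: the same sentence serves the CCSQ sum and FACT-BRM, which would fit copying. These explanations stand, so the late comparison cannot be said to rest on patients seen off schedule.

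A reader might go further and infer that forms were sorted into single seven-day weeks, that about half of the in-window forms were lost, and that this loss led to the repeated-measures ANOVA being abandoned. The documents do not support that chain. The SAP never describes such sorting, and the listed weeks could equally be nominal visit labels, under which no in-window form is lost. The protocol asks for visits as near the designated day as possible, which gives no support to an even ±7-day spread. The ANOVA was also dropped for diary compliance, which uses no questionnaire mapping. Section 5.4.1 ends all study procedures when treatment is permanently discontinued, which is another source of missing data.

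**Conclusion.** The point holds for the late time point, with moderate confidence, and should be corrected. The SAP replaced common protocol points with weeks chosen after the data were seen. The stated results are a 49/50 mismatch between items of one form and a last CCSQ sum and FACT-BRM comparison in a week that is no nominal visit in either arm under 28-day or calendar months.

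This rests on reading the SAP's weeks as study weeks counted from Day 1, and on a month of 28, 30, 30.44 or 31 days. A 29-day month would give a week-50 visit, but it displaces three other SAP weeks. If week 49 or 50 is a typing slip, the mismatch disappears and only the correction and the post hoc selection remain. Whether any in-window forms were counted as missing, and how many, is unknown. No effect on the decision to drop the ANOVA is shown.

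**What to change.** Replace frequency-based selection with one mapping rule for every item of a form and for both arms:

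1. Assign each CCSQ and FACT-BRM form by its completion date to the nearest protocol-scheduled visit, using contiguous windows. On the 28-day grid these run from 14 days before to 13 days after a maintenance visit: Days 71 to 98 around Day 85, Days 155 to 182 around Day 169, and Days 323 to 350 around Day 337. Weeks 49 and 50 then belong to one visit. Where visits are two weeks apart, the windows are correspondingly shorter.
2. If two forms qualify, keep the one closest to target.
3. Run a ±1 week window as a sensitivity analysis. It should not be the main rule, because around Day 337 it ends at Day 344 and leaves Days 345 to 350 unassigned.
4. State which scheduled visit stands for 12 months (Day 337 or Day 365 on the 28-day grid) and how end-of-study forms are mapped.
5. Report the CCSQ sum, GF7 and FACT-BRM at the same visits, with forms due and received by arm. If week 49 or 50 is a slip, correct it.

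The cost is one SAP paragraph and a re-mapping of existing forms, with no new data. It depends on completion or visit dates being available: the questionnaires reproduced in Appendices 13.1 and 13.2 show no date field. Some reported numbers of patients and medians may change.

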- g Chemistry labs will be done as clinically indicated and should include albumin, creatinine kinase (CPK), urea or blood urea nitrogen (BUN), creatinine, alanine aminotransferase (ALT), aspartate aminotransferase (AST), lactate dehydrogenase (LDH), serum alkaline phosphatase, direct and total bilirubin, glucose, total protein, sodium, potassium, chloride, bicarbonate (HCO3) (CO2; venous blood), calcium, and phosphorous. Chemistries should be performed weekly during the induction phase or according to institutional protocol. Specific individual chemistry labs may be omitted according to investigator judgment if not included in the institution's chemistry profile.
- h All Grade 3 and 4 adverse events (regardless of whether they occur on treatment or non-treatment weeks) will be collected until the last day of treatment and submitted utilizing the corresponding AE forms. Additionally, all SAEs, regardless of grade will also be collected.
-  Treatment perceptions and HRQOL data will be collected via CCSQ and FACT-BRM, respectively, at baseline, every 2 weeks during the induction phase, and monthly during the maintenance phase (beginning at day 29) for up to 1 year. These questionnaires are to be completed prior to the administration of the dose for that visit. If dose is held or changed QoL is still to be completed.
- j Patients will be instructed to record details on the receipt of HDI in the drug administration diary and will return the diary to the site at the subsequent visit. These diaries will capture the onset of AEs in relationship to the day of drug administration.

Table 3: Schedule of Events (Cohort B: PEG IFN) Suggested schedule of events (QOL evaluation is mandatory)

Test/Assessment	Pretreatment a	D1	D8 b	D15 b	D22 b	b	b	b	Maintenance Phase c
Informed consent	X								
Medical history	X								
Interferon preference questionnaire	X								
ECOG PS	X								
Weight/vital signs d		X	X	X	X				X
Physical examination e		X							X
Hematology labs f		X	X	X	X				X
Chemistry labs g		X	X	X	X				X
Collection and Monitoring of		X	X	X	X				X
Grade 3 and 4 AE and all SAEs h									
QoL evaluations i		X		X					X
Drug administration diary j		X	X	X	X				X

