#### • Secondary outcomes:

• To compare the convenience and satisfaction with chemotherapy for patients on standard HDI versus PEG IFN using a chemotherapy convenience and satisfaction questionnaire (CCSQ), with a 30% between-group difference in scores deemed clinically relevant, a mixed randomized-repeated measures ANOVA will be conducted for items CS1 – GP5 as a summation score, since these items share the same Likert scale anchors and valences. Treatment group (HDI versus PEG IFN) will comprise the randomized (betweengroup) factor and treatment period time represents the repeated measures (withingroup) factor. For the repeated measures factor of time, given the different induction phases for the two regimens (i.e., approximately 4 weeks for HDI versus 8 weeks for PEG IFN), the ANOVA will capture outcomes at baseline, 2 weeks, 3 months, 6 months and 12 months, with inclusion of the latter outcome dependent on the amount of missing data.

It should be noted that although the CCSQ is technically an ordinal tool, it will be treated as a continuous/interval scale for the purposes of the ANOVA, with transformation of outcomes as deemed appropriate. It should also be noted that the CCSQ has not been formally validated; therefore, certain items will be presented descriptively, rather than inferentially, as per the judgment of the study authors in keeping with the study's exploratory nature.

Item GF7, which assesses contentment with current quality of life, will be presented descriptively for the two treatment groups as a separate item due to its positively worded valence, at baseline, 2 weeks, 3 months, 6 months and 12 months. No inferential analyses will be conducted for this item.

For item CS10, which assesses satisfaction with current results of chemotherapy, the 3 separate "yes" responses will be collapsed for the sake of convenience and presented descriptively as a dichotomous outcome for the two treatment groups at 2 weeks, 3 months, 6 months and 12 months. No inferential analyses will be conducted for this item.

Items CS11 and CS12, which measure recommendation/choice of chemotherapy regimen, will be presented descriptively for the two treatment groups at 2 weeks, 3 months, 6 months and 12 months. No inferential analyses will be conducted for these items.

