Item CS13, which rates the chemotherapy regimen overall, will be presented descriptively for the two treatment groups at the end of the study (i.e., 12 months). No inferential analyses will be conducted for this item.

- To evaluate the treatment-related side effects that may impact the patient's health-related QoL (HRQOL) using the Functional Assessment of Cancer Therapy of Biologic Response Modifier (FACT-BRM), with a 30% between-group difference in scores deemed clinically relevant, a mixed randomized-repeated measures ANOVA will be conducted for all items as a summation score, similar to the analysis plan described for CCSQ items CS1 GP5 (page 23, second bullet point). Separate subscales will be presented descriptively for the two treatment groups.
- The frequency of Grade 3 and 4 toxicities, according to the National Cancer Institute (NCI) Common Toxicity Criteria for Adverse Events (CTCAE) for patients on standard HDI versus PEG IFN, will be presented descriptively for the two treatment groups at 2 weeks, 3 months, 6 months and 12 months. No inferential analyses will be conducted for this outcome.
- Patients' reasons for their choice of treatment with HDI versus PEG IFN, for those cases in which patients are presented with a choice of either treatment option, will be reported descriptively at the study's conclusion (i.e., 12 months). No inferential analyses will be conducted for this outcome.

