#### 9.2 Safety

The only adverse events that will be counted will be treatment-emergent Grade 3 and 4 AEs and treatment-emergent SAEs regardless of grade. These events are those that started after the start of that treatment period, or were present prior to the start of the treatment period but increased in severity, or changed from being not suspected to being suspected to be due to treatment.

Treatment-emergent adverse events will be summarized separately for each treatment group and by body system and preferred term. Any other information collected (eg, severity or relatedness to treatment) will be listed as appropriate.

Laboratory data will be summarized by presenting summary statistics of raw data and change from baseline values (means, medians, standard deviations, ranges) will be provided.

Data from other tests will be listed, notable values will be flagged, and any other information collected will be listed as appropriate. Any statistical tests performed to explore the data will be used only to highlight any interesting comparisons that may warrant further consideration.

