- Treatment-related side effects that may impact the patient's health-related QoL (HRQOL) using the Functional Assessment of Cancer Therapy of Biologic Response Modifier (FACT BRM), with a 30% between-group difference in scores deemed clinically relevant. Time points of comparison were baseline/week 1, week 3, week 13, week 25, and week 50.

- The frequency of Grade 3 and 4 adverse events (AEs), according to the National Cancer Institute (NCI) Common Toxicity Criteria for Adverse Events (CTCAE) for patients on standard HDI versus PEG IFN, and the frequency of severe adverse events (SAEs), regardless of grade.
- Patients' reasons for their choice of treatment with HDI versus PEG IFN at the study's conclusion, for those cases in which patients were presented with a choice of either treatment option.

All analyses were conducted using IBM SPSS Statistics for Windows, Version 25.0 (Armonk, NY: IBM Corp.), with $p < .05$ denoting statistical significance.

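### FACT-BRM totals are compared week by week between self-chosen arms, and the pre-dose Day 1 score is not used to adjust the later weeks

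*SAP*

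**What the plan says.** The SAP's FACT-BRM entry reads "Time points of comparison were baseline/week 1, week 3, week 13, week 25, and week 50". On method, the SAP explains that missing data led it to drop the planned ANOVA: "Therefore, we reported separate non-parametric statistical outcomes when deemed feasible". It adds that "we were unable to capture within-subject correlations over time", and that the group-by-time interaction was lost as well. It names no covariate and no change score for FACT-BRM.

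Protocol Section 9 (secondary outcomes) had planned for FACT-BRM that "a mixed randomized-repeated measures ANOVA will be conducted for all items as a summation score, similar to the analysis plan described" for the CCSQ, where "the ANOVA will capture outcomes at baseline, 2 weeks, 3 months, 6 months and 12 months". Baseline was therefore a level of the outcome there too. The same section keeps the FACT-BRM subscales descriptive and rules out inference on item GF7.

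Tables 2 and 3 (Section 6) mark the quality-of-life forms at Day 1 in both cohorts and make them mandatory. The footnotes say "These questionnaires are to be completed prior to the administration of the dose for that visit". Section 5.2 states that treatment is not randomized. For laboratory data, Section 9.2 says that "change from baseline values (means, medians, standard deviations, ranges) will be provided".

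**The concern.** The stated purpose of the FACT-BRM comparison is treatment-related side effects. Many of its items (energy, pain, sadness, worry about dying, trouble concentrating) can be present before the first dose. A raw week 13 total mixes that starting state with whatever the drug adds.

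In a randomized trial this would mainly cost precision. Here the arms are chosen, and the Interferon Preference Questionnaire (Appendix 13.3) itself lists toxicity, convenience and physician recommendation as possible drivers. A difference at the start is plausible, and the SAP applies a 0.05 significance level. A gap that existed before dosing could be read as a difference between drugs, in a pilot meant to inform whether a larger trial is warranted (Section 9.3).

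Comparing the arms at baseline makes such a gap visible. It does not take the gap out of weeks 3, 13, 25 and 50.

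**Working it through.** The documents give no power, SD or standard error for FACT-BRM, so there is no plan figure to reproduce.

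**Inputs from the documents.** N = 100 (Section 9.3); at most 60% in one arm (Section 3); significance at 0.05 (SAP; two-sided assumed).

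**Assumptions not in the documents.** Normal scores in SD units. Correlation ρ between Day 1 and a later week of 0.3, 0.5 or 0.7. Baseline gap of 0, 0.3 or 0.5 SD. Either 60 v 40 with all forms present, or 30 v 20 with half present. The SAP reports heavy missingness but no count per week.

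**Bias.** If the gap regresses toward the mean, the unadjusted later difference is biased by ρ × gap:

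| Gap | ρ = 0.3 | ρ = 0.5 | ρ = 0.7 |
|---|---|---|---|
| 0.3 SD | 0.09 | 0.15 | 0.21 |
| 0.5 SD | 0.15 | 0.25 | 0.35 |

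The unadjusted standard error at 60 v 40 is √(1/60 + 1/40) = 0.204 SD. A bias of 0.35 SD is therefore 0.35/0.204 = 1.7 standard errors.

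**False rejection with no drug effect** (4,000 simulated trials per setting, Mann-Whitney on the later score):

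| Arms | Gap | ρ = 0.3 | ρ = 0.5 | ρ = 0.7 |
|---|---|---|---|---|
| 60 v 40 | 0.3 SD | 7% | 10% | 17% |
| 60 v 40 | 0.5 SD | 11% | 21% | 38% |
| 30 v 20 | 0.3 SD | 5% | 8% | 10% |
| 30 v 20 | 0.5 SD | 7% | 13% | 21% |

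With the Day 1 score as covariate (ANCOVA or rank ANCOVA) the rate stays near 5% in every cell. Repeat runs move individual cells by about one percentage point.

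**Precision with no gap.** Residual variance after adjustment is (1 − ρ²) times the raw variance: 0.91, 0.75 and 0.51. One hundred patients then carry the information of 100/0.91 = 110, 100/0.75 = 133 and 100/0.51 = 196. Simulated power for a true 0.5 SD effect, over ρ = 0.3 to 0.7:

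| Arms | Mann-Whitney | Rank ANCOVA | ANCOVA |
|---|---|---|---|
| 60 v 40 | about 66% | 70-90% | 72-92% |
| 30 v 20 | about 38% | 41-60% | 43-64% |

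**Why not a change score.** Its variance factor is 2(1 − ρ): 1.4, 1.0 and 0.6. It gains precision only when ρ exceeds 0.5, whereas the covariate gains whenever ρ is above zero.

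**Where adjustment falls short.** If the groups keep a constant gap instead of regressing, ANCOVA removes ρ × gap and leaves (1 − ρ) × gap. At 60 v 40 with gaps of 0.3 to 0.5 SD and ρ of 0.3 to 0.7, the adjusted test then rejects in about 9% to 41% of trials. The unadjusted test rejects in about 29% (0.3 SD) and 64% (0.5 SD).

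**The case against.** The study is an exploratory pilot. The SAP admits that it lost the within-patient link and asks for cautious reading. It tested only where it judged that feasible, so a FACT-BRM test at every listed week is not established. Missing data were the reason for abandoning the model. All of this is fair and limits the weight of the point. But the caveat corrects nothing, and descriptive medians carry the same gap as a test. A model for one week needs only that week's form and the Day 1 form, so the reason for dropping the five-level ANOVA does not rule it out.

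Some stronger readings are tempting, and the documents do not support them:

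- A reader might infer that Day 1 adjustment restores a 5% error rate. That holds only if the Day 1 score carries all the confounding, and the constant-gap result shows otherwise.
- A reader might take the figures for 100 complete forms as the expected size. The SAP's own account of missingness makes the 30 v 20 rows at least as relevant.
- A reader might add that one pre-dose level among five dilutes the ANOVA group effect by 20%. That concerns only the main effect of an analysis the SAP has dropped, and its interaction term could have shown change from baseline.
- A reader might extend the models to the subscales and GF7. Protocol Section 9 keeps both descriptive, and GF7's last SAP time point is week 49, not week 50.
- A reader might treat the laboratory rule in Section 9.2 as a precedent. It is a descriptive summary, not covariate adjustment.

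**Conclusion.** The point holds for the FACT-BRM total. A score scheduled before the first dose in both cohorts is used only as another comparison, and nothing separates a pre-treatment gap from an on-treatment difference. The direction follows from the design: bias if the self-chosen arms start apart, and lost precision whenever scores correlate over time.

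The size is conditional. It ranges from negligible (weak correlation, small gap, half the forms missing) to serious (strong correlation, 0.5 SD gap, all forms present). The documents do not show that a gap occurred, so they do not support calling any reported FACT-BRM difference an artefact. Adjustment lowered the false-rejection rate or left it near 5% wherever a gap was simulated. It removes only the confounding that the Day 1 score carries and leaves non-random missingness untouched. For an exploratory secondary outcome, this is a change that should be made, not one on which the study stands or falls.

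**What to change.** For the FACT-BRM total only:

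- Report the Day 1 score by arm as a baseline characteristic, not as an outcome time point.
- At weeks 3, 13, 25 and 50, wherever a test is judged feasible, estimate the arm difference with the patient's own Day 1 score as covariate. Use rank ANCOVA to stay non-parametric, or ANCOVA with a 95% confidence interval.
- Show the unadjusted comparison beside it, and give the number of patients in each. Patients without a Day 1 form appear only in the unadjusted one, so repeat that comparison in patients with both forms to separate the effect of adjustment from the effect of losing patients.
- State the two limits: residual confounding and non-random missingness.

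Keep the subscales and GF7 descriptive; change from Day 1 may be shown. Leave the CCSQ sum CS1-GP5 unadjusted, because its items ask about experience of chemotherapy and a pre-dose answer does not describe the treatment.

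The cost is one or two SAP sentences and at most four models, with no new data. The SAP is written in the past tense, so the adjusted results should be labelled as added after the data were seen if that is the case.
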